8.2 Methods and Timing for Assessing, Recording, and Analyzing, Managing Safety Parameters

8.2.1 Methods and Timing of Assessment

Adverse events may be discovered during regularly scheduled visits or through unscheduled patient contacts between visits. Adverse events related to study procedures would be assessed during the index hospitalization and at each study visit. They will be recorded on study data forms whether or not they are thought to be associated with the study.

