Following 2-4 weeks of home PT (T1), the participant will be fitted with the IDEO and engage in four weeks of Post-IDEO PT at the study center. During these 4 weeks, adjustments to the brace will be made and the participants will learn how to optimize the use of the brace.

At the end of the four weeks of post-IDEO PT (T2), performance testing will be repeated and overall satisfaction with the device assessed. The purpose of these assessments is to measure any immediate gains in function. Participants will then be formally ‘discharged’ from the PRIORITI program. They will be given the number of the Study Site Orthotist to call if any concerns arise with the IDEO and its fit. The costs associated with all visits to the orthotist during the 12 month follow-up period will be covered by the study.

At 6 months following the completion of the PRIORITI program (T3), participants will be contacted by the Study Coordinator and asked to participate in a brief interview by phone. The main purpose of this phone call is to keep participants engaged in the study and motivate them to come back to the hospital for the final visit at 12 months. We will also use this opportunity to ask them questions about their functioning, satisfaction with the brace and use of services (overall and specific to the IDEO). This interview will last about 15 minutes. During the call the he coordinator will remind the participant of the 12 month follow up visit. If the participant is living outside of the research site area, the coordinator will inform the participant that travel expenses can be covered for the 12 month follow up visit. (See appendix K).

At 12 months following the completion of the PRIORITI program (T4), participants will be asked to return to the Study Center to repeat the performance tests and self reported measures of outcome and satisfaction with the IDEO. Additional questions regarding use of services (overall and specific to the IDEO) will also be asked.

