5.1.1 Participant Inclusion Criteria

1. Ages 18-60
2. Currently one or more years out from a traumatic unilateral lower extremity injury at or below the knee

3. Healed fractures and able to fully weight bear
4. Evidence of either:
 - a. Weakness of ankle dorsiflexors and /or plantarflexors resulting from leg injury (defined as less than 4 out of 5 on manual muscle test)
 - b. Limited ankle dorsiflexion (< 10 degrees) and /or limited ankle plantarflexion (< 20 degrees) resulting from leg injury
 - c. Mechanical pain with loading to hindfoot/midfoot (\geq 50 mm on a 0-100 mm visual analogue scale assessing average daily pain)
 - d. Ankle or Hindfoot fusion or candidate for ankle or hindfoot fusion
 - e. Candidate for amputation secondary to ankle/foot impairment

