7.2 Physical Therapy Protocol. As indicated above, participants enrolled in PRIORITI will participate in the Return to Run physical therapy regimen. During Phase 1 (pre-IDEO) participants will engage in a home physical therapy program as prescribed by the study team for 2-4 weeks. During Phase 2 (post-IDEO), participants will receive 3 sessions of PT a week for an additional 4 weeks. Participants will be encouraged to test the IDEO under load in real world

conditions and report their experience to the study team. Each PT session will last for approximately 90 minutes. During phase 2, participants will be encouraged to complete home exercises to complement the therapy they are receiving in the clinic.

To help ensure standardization of the PT protocol across centers, several procedures will be put in place. *First*, the PTAs providing the pre-IDEO and post-IDEO physical therapy must have some documented training in sports medicine and experience working with limb trauma patients. They will be trained in the PT protocol at a 3-day training at the Center for the Intrepid in San Antonio. The 3 days will be devoted to the PT protocol with ample use made of demonstrations and practice sessions. As mentioned above, training videos will be produced and provided to the PTs or PTAs for reference. *Second*, the PTAs will be required to document the therapy provided at each session. This documentation will be reviewed on an ongoing basis by the investigators to assure the fidelity of the intervention. *Third*, the PTAs will participate in bi-weekly video conference calls together with [name] at which time individual cases will be reviewed and difficulties in providing the PT and keeping patients engaged in the program will be discussed.

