APPENDIX C: DATA COLLECTION SCHEDULE

	TIME 0	T2	T3	T4
Assessment	Baseline			
Patient Characteristics				
Demographics	X			
Marital Status & Social Support (MSPS)	X			
Self Efficacy	X			X
Income (past year) & Health Insurance	X			X
Injury Characteristics				
Mechanism, Type, Side of Injury	X			
Classification of Fx (AO/OTA & Gustilo)	X			
Other limb and non limb injuries	X			
Medical History and Clinical Assessment				
Height and Weight	X			X
Co-morbidities & Smoking History	X			
Fracture Healing	X			
Evidence of PTOA (from x-rays)	X			
ROM and Strength of Lower limbs	X			X
VAS Pain and Use of Narcotics	X			X
Outcomes: Performance Assessments				
4 Square Step Test	X	X		X
Illinois Agility Test	X	X		X
Sit to Stand	X	X		X
Timed Stair Ascent	X	X		X
Self Selected Walking Speed	X	X		X
Shuttle Run	X	X		X
Single Leg Stance	X	X		X
Outcomes: Self Reported Measures				
Short Musculo Func Assess (SMFA)	X		X	X
Veterans Health Survey (VR-12)	X		X	X
Paffenbarger Activity Scale (PPAQ)	X			X
Brief Pain Inventory (BPI)	X			X
Usual Major Activity Status	X		X	X
If working: Work Productivity (WPAI)	X		X	X
Depression Scale of PHQ (PHQ-9)	X			X
PTSD Checklist (PCL)	X			X
Use and Satisfaction with IDEO				
Satisfaction with Brace (OPUS & CFI)	X	X	X	X
Use of Brace, Shoe Wear , Ambulatory Aids	X	X	X	X
Use of Services and Aids				
Hospitalizations	X		X	X
Orthotic Services	X		X	X
PT/OT Services	X		X	X
Other Services	X		X	X
Treatment Logs Maintained by CPO & PTs				

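### Section 8.2.1 ties adverse-event assessment to an index hospitalization this outpatient study does not have, and its per-visit commitment is not carried into the visit lists, Appendix C or the PT records

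*Combined protocol and SAP*

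**What the plan says.** Section 8.2.1 makes three statements. On discovery: "Adverse events may be discovered during regularly scheduled visits or through unscheduled patient contacts between visits". On timing: "Adverse events related to study procedures would be assessed during the index hospitalization and at each study visit". On recording: "They will be recorded on study data forms whether or not they are thought to be associated with the study".

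The population is defined in Section 5.1.1: "Currently one or more years out from a traumatic unilateral lower extremity injury at or below the knee". Sections 4 and 7.2 describe 2-4 weeks of home PT, brace fitting at T1, and four weeks of PT at the study center (three sessions a week, about 90 minutes each). T2 testing follows, then a phone interview at 6 months (T3) and a return visit at 12 months (T4).

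On the PT-session records, Section 7.2 says: "This documentation will be reviewed on an ongoing basis by the investigators to assure the fidelity of the intervention". For the year after T2, Section 4 says of participants: "They will be given the number of the Study Site Orthotist to call if any concerns arise with the IDEO and its fit". Of T3 it says: "The main purpose of this phone call is to keep participants engaged in the study", and it adds that questions on function, brace satisfaction and service use will be asked. Appendix C ends with an unticked line, "Treatment Logs Maintained by CPO & PTs".

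Section 8.1.3 includes, in its definition of a serious adverse event, unanticipated events from the rigor of the PT program and events arising from the fit or wear of the brace.

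**The concern.** The timing rule appears to have been written for a study that starts with an acute admission. Here the only injury admission lies before enrolment, and Section 6.2 refers to it only as a source of old records. The contacts at which this intervention could do harm (first fitting, supervised high-intensity PT, and then a year of brace wear) are not named in its place.

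This matters because the study has no control arm. If one site asks at every PT session and another waits for complaints, no comparison in the design can correct the difference. Other protections are limited: Section 9.2.1 says no DSMB is required and relies on the Medical Monitor, Sections 8.7 and 8.8 set no halting or stopping rules, and Section 8.3.1 lets sites report some events locally without informing the Coordinating Center. The 72-hour reporting period in Section 8.3.2 begins only when someone becomes aware of an event.

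**Working it through.** There is no power or event-rate figure to reproduce. The check sets Section 8.2.1 beside each contact and its listed content.

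| Contact | Covered by 8.2.1? | Adverse-event item in the listed content |
|---|---|---|
| Index hospitalization | Named, but does not occur | Not applicable |
| T1 fitting | Not named; absent from the follow-up schedule in 6.3 | No T1 column in Appendix C |
| Post-IDEO PT sessions | Not named | 7.2 asks only for a record of the therapy given |
| T2 | Yes, as a study visit | None in 6.3.1, 6.3.3 or Appendix C |
| T3 call | Unclear | None in 6.3.4 (T3 interviews) or Appendix C |
| Call to the orthotist, T2 to T4 | Only as an unscheduled contact | No forwarding rule stated |
| T4 | Yes, as a study visit | None in 6.3.1, 6.3.2, 6.3.5 or Appendix C |

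**Status of T3.** Section 6.3 lists T3 in the follow-up visit schedule and Appendix K titles it a visit. Section 4 describes a phone interview of about 15 minutes. Both readings are open.

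**Size of the unnamed supervised exposure** (Section 7.2; enrolment from Sections 4, 5.1 and 10.2):
- Sessions per participant: 3 per week x 4 weeks = 12.
- All participants: 12 x 85 = 1,020. With the 90 in the Protocol Summary it would be 12 x 90 = 1,080.
- Time per participant: 12 x 90 minutes = 1,080 minutes, or 18 hours.

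**Recall.** T2 to T4 is 12 months. If T3 carries an adverse-event query, the longest interval between scheduled queries is about 6 months. If it does not, the interval is about 12.

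**Scope.** The timing sentence in 8.2.1 limits assessment to events related to study procedures, while the next sentence records events regardless of association. Someone following the first could decide relatedness before asking, which defeats the second.

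**Route for brace problems.** Section 8.1.3 places brace-fit events under serious adverse events. Section 4 sends fit concerns to the Study Site Orthotist. Section 8.3.2 requires reporting through a REDCap form. Nothing connects the orthotist's call to that form.

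**The case against.** The strongest reply is that Section 8.2.1 does not stop at the hospitalization. Its second clause requires assessment at each study visit. T2 falls at the end of the brace and PT phase and T4 at 12 months, so a reader who inferred that harms are actively sought neither during exposure nor in the following year would be contradicting the text. That reply stands.

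Nor can one infer that no form asks about adverse events. The contents page lists draft case report forms, but neither they nor the treatment logs are in the available document. Section 8.2.1 says events go on study data forms, Section 13.3 names adverse events as a data type, and Section 8.3.2 refers to a form for serious events and unanticipated problems. The lists and Appendix C show that nothing is scheduled, and no more than that.

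There are also partial safeguards:
- Section 8.2.1 allows discovery at unscheduled contacts, which could include a call to the orthotist, who is trained for the study.
- Section 7.2 encourages participants to tell the study team how the brace performs under load, and provides for case review on bi-weekly calls.
- The retention section promises contact by mail and phone during the year.
- T3 and T4 ask about hospitalizations and service use, and the OPUS satisfaction items cover pain with use, comfort and fit.

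These lower the chance of missing an event that led to care. They remain utilization, satisfaction and retention contacts, and none is stated to produce an event graded and attributed as Section 8.2.2 requires. Finally, no objective or endpoint estimates a harm rate, so no planned result would be directly biased. That is fair and limits the severity.

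**Conclusion.** The point holds in limited form. One of the two settings in the timing rule is empty. The other secures T2 and T4 but leaves T1 and 12 PT sessions per participant unnamed and T3 ambiguous. The commitment does not appear in the listed visit content, Appendix C or the PT-record requirement, and brace concerns after T2 have no stated path to the coordinator.

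The likely consequence is under-ascertainment, or capture that varies by site. Its size cannot be estimated, because the documents give no expected event rate and the forms are not visible. The 1,020 sessions measure unnamed contact, not missed events, and assume 85 participants with full attendance. If the unseen forms and logs already carry adverse-event questions, the remaining fault is wording and a schedule that does not match practice.

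Power and the primary tests are unaffected. This should be corrected, but it is not a defect that undermines the study's main conclusions.

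**What to change.** 1. In Section 8.2.1, replace the reference to an index hospitalization with the study's own contacts: T1 fitting, post-IDEO PT sessions, T2, the T3 call and T4.
2. In the same sentence, remove the restriction to procedure-related events, so that assessment matches the recording rule that follows it.
3. Add an adverse-event row to Appendix C for these contacts, including T1, which has no column now, and one scripted adverse-event question to the T3 call.
4. Add a yes/no adverse-event field to the logs the orthotists and therapists already keep. Require any yes, and any brace-related call from a participant, to be passed to the coordinator for the adverse-event form.

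If the case report forms or logs already contain such questions, steps 3 and 4 reduce to citing them. The cost is protocol wording, one schedule row, one question and one log field. The downside is that more minor events will be recorded, with slightly more data entry. The change concerns data collection only and sets no rule for treating participants.

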8.2.2 AE/SAE Grading and Relationship Assignment

Adverse event grading: Adverse events will be graded using standard criteria. The study physician will determine relationship of event to the study procedure.

GRADE 1 (Mild) Transient or mild discomfort (< 48 hours); no medical intervention/therapy required

GRADE 2 (Moderate) Mild to moderate limitation in activity - some assistance may be needed; no or minimal medical intervention/therapy required

GRADE 3 (Severe) Marked limitation in activity, some assistance usually required; medical intervention/therapy required, hospitalizations possible

GRADE 4 (Life-threatening) Extreme limitation in activity, significant assistance required; significant medical intervention/therapy required, hospitalization or hospice care probable.

Relationship Assignment The relationship of the adverse event to participation in the study will be assessed as either:

Definitely related
Probably related
Possibly related
Unlikely related
Unrelated

8.2.3 Recording and Documentation

Sites will maintain source documents including but not limited to (laboratory and radiology reports, clinical notes and discharge summaries). After review of initial and final reports by the medical monitor, the events may be reclassified at their discretion.

8.2.4. Management of Adverse Events

Adverse Events and Serious Adverse Events will be managed according to protocol guidelines. If specific guidelines do not exist, AEs/SAEs will be managed according to the medical judgment of the treating physician.

8.3 Adverse Event Reporting Procedures

8.3.1 Local Reporting Requirements.

Study sites must always follow and comply with their own local institution's adverse event reporting requirements, which may differ from those adopted by the PRIORITI Study. Depending on the local requirements, a site may report events locally and not report those events to the METRC Coordinating Center. Each participating site is responsible for ensuring that all local IRB requirements for reporting adverse events (both internal and external) are met.

8.3.2 SAE and Unanticipated Problem Reporting Requirements

All Serious Adverse Events that are Unexpected AND related or possibly related to the study must be reported to the Medical Monitor and METRC Coordinating Center within 72 hours of being made aware of the event.

In addition, Unanticipated Problems (UPs) that are not adverse events must also be reported to the METRC Coordinating Center within 14 calendar days after the event has been discovered.

SAEs/UPs will be reported to the METRC Coordinating Center by entering the SAE/UP form into REDCAP. REDCap is programmed to automatically send an email to the Coordinating Center for both SAEs and Ups, and to the Medical Monitor in the case of an SAE.

The Medical Monitor for this study is:

[name], FACS
Department of Orthopedic Surgery
[name]
[name]
[contact]
[contact]
E-mail: [contact]

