8.1.3 Serious Adverse Event

A serious adverse event is defined as:

1. Death
2. Unanticipated events related to rigor of participating in the Return to Run PT Program; or events related to IDEO brace fit or wear.
3. Other events that are unexpected AND serious AND related or possibly related to the study

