9.2 Safety Monitoring Plan

9.2.1 Safety Review Plan by the DSMB

A DSMB is not required for this study. A Medical Monitor has been appointed and will review any SAEs, unanticipated problems involving risk to participants or others and all deaths.

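### Sections 8.3.2, 8.3.3 and 8.5 do not guarantee that every event section 9.2.1 assigns to the Medical Monitor reaches the Monitor in a set time, notably deaths judged unrelated or expected and some unanticipated problems

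*Combined protocol and SAP*

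**What the plan says.** Section 9.2.1 says that no DSMB is required and gives the review task to one person: "A Medical Monitor has been appointed and will review any SAEs, unanticipated problems involving risk to participants or others and all deaths".

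Section 8.3.2 sets the reporting duty. For SAEs it reads: "All Serious Adverse Events that are Unexpected AND related or possibly related to the study must be reported to the Medical Monitor", with the Coordinating Center as second recipient and a limit of 72 hours. Unanticipated problems that are not adverse events "must also be reported to the METRC Coordinating Center within 14 calendar days after the event has been discovered"; the Monitor is not named there. Both kinds of report are made by entering a form in REDCap. REDCap then e-mails the Coordinating Center for either kind, "and to the Medical Monitor in the case of an SAE".

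Four other sections bear on the point:

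- Section 8.1.3 defines an SAE. Item 1 is death, without condition. Item 2 covers unanticipated events from the rigor of the therapy program, then "events related to IDEO brace fit or wear". Item 3 is "Other events that are unexpected AND serious AND related or possibly related to the study".
- Section 8.3.1 allows that, depending on local requirements, "a site may report events locally and not report those events to the METRC Coordinating Center".
- Section 8.3.3 has the Coordinating Center circulate reports it has received on events judged reportable, as appropriate and under consortium policy, with copies to the Monitor.
- Section 8.5 requires a final report on an SAE to the Monitor and the Coordinating Center once the event has been followed to resolution. It sets no time limit.

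**The concern.** The review scope in section 9.2.1 is wider than the timed reporting duty in section 8.3.2. Section 8 says the Monitor oversees safety by reviewing SAE reports, so the review is only as complete as the reports that arrive.

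Section 8.2.3 lets the Monitor reclassify events after seeing the initial and final reports. That check loses force if the site's own view of relatedness and expectedness settles whether an initial report must be sent at all. Halting rules, individual stopping rules and interim analysis are all marked not applicable (sections 8.7, 8.8 and 10.5), so little else at study level would pick up a missed event. The Protocol Summary does describe a DSMB, which conflicts with section 9.2.1. Even there, it is the Monitor who may convene it over SAEs, so the same reports matter.

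What is at stake is the completeness and timeliness of safety oversight. The efficacy estimates are not affected.

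**Working it through.** No arithmetic applies. The check takes each type of event in turn and asks two questions: does section 9.2.1 promise its review, and which section brings it to the Monitor, by when?

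| Event | Review promised in 9.2.1? | Route to the Monitor | Time limit |
|---|---|---|---|
| SAE, unexpected and at least possibly related | Yes | 8.3.2 duty | 72 hours |
| Death judged unrelated or expected | Yes, as an SAE and as a death | REDCap e-mail if an SAE form is entered; 8.5 final report | None |
| Expected brace fit or wear event, if 8.1.3 item 2 makes it an SAE | Yes, on that reading | As for the row above | None |
| Unanticipated problem that is not an adverse event, involving risk | Yes | Coordinating Center within 14 days, then 8.3.3 copy if judged reportable | None for the Monitor |
| Unanticipated problem that is a non-serious adverse event (outside 8.1.3 item 2) | Yes, if it involves risk | No explicit rule in 8.3.2 | None |
| Non-fatal serious event judged unrelated, outside 8.1.3 item 2 | Not as an SAE, because 8.1.3 item 3 excludes it | Not applicable | Not applicable |

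**Deaths.** A death judged unrelated or expected fails the filter in section 8.3.2. It cannot enter as an unanticipated problem either, because section 8.1.2 requires an event to be both unexpected and at least possibly related. The Department of Defense route in section 8.3.4 is also limited to deaths related to participation. That leaves the REDCap e-mail and the final report.

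**The REDCap e-mail.** It carries no filter of its own, but it is triggered by a form. Section 8.3.2 can be read in two ways. If every SAE must be entered, that conflicts with the filter in the section's opening sentence. If only the filtered SAEs must be entered, the e-mail adds nothing for the others. The text does not settle which is meant.

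**Brace fit or wear.** In section 8.1.3 item 2 it is unclear whether the word unanticipated governs the second half. If it does not, an expected fit or wear event is an SAE that section 8.3.2 does not require to be sent.

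**Unanticipated problems.** One that is also an SAE meets the 72-hour filter by definition. One that is not an adverse event goes to the Coordinating Center, and the copy in section 8.3.3 is qualified twice: as appropriate, and judged reportable. One that is a non-serious adverse event falls between the two sentences of section 8.3.2, since the first covers SAEs and the second covers problems that are not adverse events.

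**The case against.** The strongest reply is that the protocol has more routes than the opening sentence of section 8.3.2. REDCap notifies the Monitor of an SAE without regard to expectedness or relatedness. Section 8.3.3 copies reportable events to the Monitor. Section 8.5 requires a final SAE report, also unfiltered. Section 8.2.3 lets the Monitor overrule a classification. Sites record adverse events whether or not they are thought related (section 8.2.1), and site monitors review participant records (section 9.1).

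Most of this stands, and it rules out three stronger readings that a reader might infer:

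- *That the promised review cannot take place, or that the Monitor receives only unexpected and related SAEs.* The routes above contradict this. What is missing is a guarantee and a time limit.
- *That expected or unrelated SAEs in general escape review.* Section 8.1.3 item 3 already limits other SAEs to unexpected and at least possibly related events. Outside the filter there remain mainly deaths, and perhaps expected fit or wear events.
- *That section 8.3.1 lets a site withhold an event that section 8.3.2 says must be reported.* It says local rules may differ and that some events may stay local. It does not say that it overrides the duty.

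The reply does not close the gap. The e-mail needs a form that section 8.3.2 does not clearly require, the copy depends on a judgment of reportability and on the report having reached the Coordinating Center, and the final report has no deadline. Recording an event at the site is not the same as sending it to the Monitor.

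**Conclusion.** The mismatch is real and limited. Section 9.2.1 promises review of events for which no section guarantees timely reporting to the Monitor. The clearest case is a death judged unrelated or expected. Next come unanticipated problems that are not adverse events, where the route is conditional, and those that are non-serious adverse events, where section 8.3.2 is silent. Expected fit or wear events belong on the list only on one reading of section 8.1.3 item 2.

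The size cannot be put in numbers, because the documents give no expected event counts. The conclusion rests on the protocol text alone; the consortium policies and manual to which it refers might set further reporting rules, but they are not part of the documents. The documents do not call the Monitor independent, and the Protocol Summary still describes a DSMB, so the Monitor is best described as the study-level reviewer named in section 9.2.1. The point should be corrected because it concerns safety oversight and the correction is cheap.

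**What to change.** Reconcile section 8.3.2 with section 9.2.1, and with sections 8.1.3, 8.3.3 and 8.5:

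1. Require that all SAEs as defined in section 8.1.3, including every death, and all unanticipated problems involving risk be entered in REDCap and sent to both the Medical Monitor and the Coordinating Center within a stated time, whatever the site's view of relatedness or expectedness.
2. Keep the unexpected-and-related filter for expedited onward reporting only.
3. Add unanticipated problems to the REDCap e-mail that goes to the Monitor.
4. State that section 8.3.1 does not override this duty.
5. Make clear in section 8.1.3 item 2 whether expected fit or wear events are SAEs.

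The cost is about one paragraph, a clarifying phrase and one notification setting, plus a few more reports for the Monitor to read. The change has a limit: for other non-fatal events the site's judgment also sits inside the SAE definition (section 8.1.3 item 3), and rewriting section 8.3.2 does not alter that.
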